Subjects will be withdrawn from the study in the event of:

1. Consent is withdrawn by the patient.
2. Patients will be withdrawn from the study if they experience intolerable or excessive side effects due to the probiotics.

Subject drop out is predicted at 10% and is taken into consideration in the sample size calculation.

7. Study Intervention

Patient will be randomized into a treatment or control group. No other treatments such as laxatives or enemas are given to all patients.

1. Treatment group.
 - a. Each patient will receive probiotics in form of granular powdered microbial cell preparation (Hexbio®) – Specialized formulation of six microbial strains containing:
 - i. Lactobacillus acidophilus BCMC® 12130
 - ii. Lactobacillus casei BCMC® 12313
 - iii. Lactobacillus lactis BCMC® 12451

- iv. Bifidobacterium bifidum BCMC® 02290
- v. Bifidobacterium infantis BCMC® 02129
- vi. Bifidobacterium longum BCMC® 02120

b. Dosage: 1 sachet twice a day after meals for 1 week.

2. Control group

- a. Each patient will receive placebo sample of similar appearance and composition but do not contain probiotics.

8. Efficacy, Safety and Other Assessments

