8.2 Safety

Patients will be counseled that generally safety profile of probiotics seems to be good. Based on the available trials, no adverse effects were noted. There might be a concern issue of safety in immune-compromised patients or those critically ill, which they will be excluded in this study.

Patients will be withdrawn from the study if they experience intolerable or any possible excessive side effects due to probiotics.

9. Assessment variables and methods of assessing.

9.1 Targeted patients will be assessed with a questionnaire (Appendix C) on gastrointestinal symptoms, well-being and stool habits. The stool consistency will be scored by a seven-point scale according to the Bristol Stool Form Scale (Appendix B). Severity of constipation will be categorized into four groups (severe, moderate, mild and no symptoms). Symptoms specifically

related to constipation such as bloating and flatulence will be recorded in detail. Severity of symptom is measured by Likert score of frequency (Very frequently, frequently, occasionally, rarely and never).

9.2 Each individual patient will be required to fill in the questionnaire at the beginning of the trial. Subsequently, patient will be required to fill up the stool chart and recorded their symptoms in a given dairy daily during the study period. Training on how to use and record the dairy will be conducted upon embarking into the study. A contact number will be advised to the participants to aid their understanding. The dairy will be collected at day 7 upon completion of the study.

Other assessment

1. Assessment of the presence of underlying medical illness will be done at the initial presentation, assessed by questionnaire about the medical history and physical examination.

10. Study conduct

10.1 Elderly patients attending medical/surgical clinics or being admitted to the medical/surgical wards PPUKM will be screened. Those with underlying medical illnesses and suspected to have constipation are selected. Random selection of the participants either for intervention group or control will be pre-determining during screening.

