APPENDIX D

[figure not shown]
EVALUATING THE EFFECT OF PROBIOTICS IN CHRONIC CONSTIPATION ELDERLY PATIENTS WITH MULTIPLE CO-MORBIDITIES

QUESTIONNAIRES

[figure not shown]
Study Number:

Patient's Sticker:

[figure not shown]
1. How frequent is your bowel movements per week?

[figure not shown]
2. Do you need assistance in evacuation? (enema/digital-manual maneuvers)

[figure not shown]
3. Do you have sensation of anorectal obstruction/ blockage?

[figure not shown]
4. Feeling of incomplete evacuation?

[figure not shown]
5. Do you have lumpy or hard stools?

[figure not shown]
6. Any straining or squeezing on defecation attempts?

[figure not shown]
1. How long have you had constipation?

[figure not shown]
2. Do you have bloating in your stomach?

[figure not shown]
3. Do you have flatulence?

[figure not shown]
4. Do you have stomach cramps?

[figure not shown]
5. How many unsuccessful attempts of evacuation within 24hours?

6. Do you have abdominal pain?

7. How long do you spend in the lavatory per attempt? (minutes)

Statistical analysis Plan

The collected data was analysed using IBM SPSS Statistics for Windows version 21.0 software (IBM Corp., Armonk, NY, USA) and Microsoft Office Excel 2010software (Microsoft, Redmond, WA, USA). Statistical significance was set at $p = <0.050$.

All of the data was assessed for normality via the usual processes.

The baseline characteristic differences between the two groups were evaluated using the Mann-Whitney U and chi-squared tests. The median results of the improvement in stool frequencies and stool consistency between the treatment and placebo group were compared using the Mann-Whitney U test. The constipation-related symptom improvements were analysed using the chi-squared test.

Intention to treat analysis was used in this trial, where only the final results within the group which they were randomized, receiving the treatment and completed the treatment assignment were analysed. Participants who deviates from the protocol as being non-compliance or withdrew consent were not included into the analysis.

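### The analysis that the SAP calls intention to treat is a completers-only analysis, so patients can be dropped for a reason linked to the constipation outcome

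*Combined protocol and SAP*

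**What the plan says.** The last paragraph of the SAP names the analysis: "Intention to treat analysis was used in this trial, where only the final results within the group which they were randomized". The same sentence then narrows the set, so that only patients "receiving the treatment and completed the treatment assignment were analysed". It adds: "Participants who deviates from the protocol as being non-compliance or withdrew consent were not included into the analysis". Non-compliance is not defined, and no rule is given for early leavers or missing diary days.

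Stool frequency and consistency are compared by Mann-Whitney U. For symptoms, "The constipation-related symptom improvements were analysed using the chi-squared test".

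Section 7 sets a one-week course and says "No other treatments such as laxatives or enemas are given to all patients". Section 6 lists two reasons for withdrawal. One is withdrawn consent. The other is: "Patients will be withdrawn from the study if they experience intolerable or excessive side effects due to the probiotics". Section 8.2 repeats the second in slightly broader words: "Patients will be withdrawn from the study if they experience intolerable or any possible excessive side effects due to probiotics". On numbers, section 6 says only: "Subject drop out is predicted at 10% and is taken into consideration in the sample size calculation".

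Sections 9.2 and 10.5 have the diary collected on day 7, at completion. The diary in Appendix B, as far as it can be read, has no field for laxative or enema use. Appendix D asks about enema or manual help, but sections 9.2 and 10.4 place the questionnaire at the start.

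**The concern.** Intention to treat means that everyone randomised is analysed in the assigned arm. The SAP's definition removes anyone who did not complete, did not comply or withdrew consent. A reader of the results would take a completers-only comparison for one protected by randomisation.

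The exclusion is not obviously harmless here. Patients enter because they are constipated, the outcome is how constipated they are over seven days, and no other bowel treatment is given. A patient who gives up because nothing is happening is excluded as a non-completer or as having withdrawn consent. A patient who takes every sachet plus a laxative may be excluded as a deviator or kept as a completer whose stools are credited to the study product. The SAP does not say which, and the readable diary would not show it. Either way, who is analysed, or what is counted, can depend on the outcome.

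**Working it through.** **Reading the text.** The SAP definition requires three things: randomised to the group, treated, and completed. Intention to treat requires only the first, so label and definition conflict for any reason for leaving.

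**No plan figure to reproduce.** The readable text gives no sample size, effect size, standard deviation or event rate. Of the inputs below, only the 10% dropout and the 7 days come from the documents. The rest are assumptions chosen to show a range.

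**1. Stool counts, one leaving rule.** Assume Poisson counts with mean m a week (the SAP's variable is the improvement in frequency; a common baseline is assumed). A share q of patients with no stool in days 1 to 4 leave. Such a patient's expected weekly total is 3m/7.

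- Loss = q·exp(−4m/7)
- Completer mean = [m − loss·3m/7] / (1 − loss)

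Take m = 3 (probiotic) and 2 (placebo), a true difference of 1.00. Then exp(−12/7) = 0.180 and exp(−8/7) = 0.319.

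| q | Loss, probiotic / placebo | Completer means | Difference |
|---|---|---|---|
| 0.1 | 1.8% / 3.2% | 3.031 / 2.038 | 0.99 |
| 0.4 | 7.2% / 12.8% | 3.133 / 2.167 | 0.97 |
| 1.0 | 18.0% / 31.9% | 3.377 / 2.535 | 0.84 |

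The middle row averages 10.0% loss, so it supposes that all predicted dropout is of this kind. The last row is an upper extreme with about 25% lost.

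**2. No true effect (m = 2 in both arms).**

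- q of 0.4 in both arms: bias 0.
- q of 0.4 v 0.2 (12.8% v 6.4% lost): 2.167 − 2.078 = 0.09 in favour of the arm that lost more.
- q of 0.4 v 0 (12.8% v none): 2.167 − 2.000 = 0.17, same direction.

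**3. A harsher model: exactly the worst responders leave.** With improvement standard normal and the lowest fraction d removed, the remaining mean is φ(z)/(1 − d), where Φ(z) = d.

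- No effect, 15% v 5% lost: 0.274 − 0.109 = 0.17 SD. With 20% v none: 0.35 SD. Both favour the arm that lost more.
- Simulated two-sided Mann-Whitney type I error (4,000 trials) at 15% v 5% is about 0.14, 0.18 and 0.25 with 40, 60 and 100 per arm, against about 0.05 with everyone analysed. Equal 10% loss already gives about 0.08 in this set-up, so not all of the excess comes from the imbalance.
- True benefit 0.5 SD with one threshold (5.8% v 14.2% lost): 0.623 − 0.262 = 0.36 SD. A true 0.3 SD falls to 0.22 SD.

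**4. Symptom test.** Assume 40 per arm, 25 v 16 improved, and 8 leavers, none improved. χ² = N(ad − bc)² divided by the product of the four margins; the corrected form replaces |ad − bc| by |ad − bc| − N/2.

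| Leavers, probiotic / placebo | Completers | p, uncorrected | p, corrected |
|---|---|---|---|
| 6 / 2 | 25/34 v 16/38 | 0.007 | 0.014 |
| 4 / 4 | 25/36 v 16/36 | 0.032 | 0.057 |
| 2 / 6 | 25/38 v 16/34 | 0.109 | 0.173 |
| All randomised | 25/40 v 16/40 | 0.044 | 0.074 |

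The SAP does not say whether a continuity correction applies. In both columns the completers result moves with who left, while the all-randomised result does not. Which values fall below 0.05 depends on the unstated choice.

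**5. Would worst rank repair the Mann-Whitney test?** The index is P(T > P) + ½P(tie), under the model of step 1.

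| Case | Truth | Completers | Worst rank for leavers |
|---|---|---|---|
| 3 v 2, q = 0.4 | 0.669 | 0.666 | 0.662 |
| No effect, q = 0.4 v 0.2 (index for the arm losing more) | 0.500 | 0.519 | 0.484 |

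Worst rank is further from the truth in the first row. In the second it errs the other way by about the same amount.

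**The case against.** The strongest reply is that the numbers are small. Under one leaving rule the loss is 0.03 of a stool even if all predicted dropout is constipation-driven, and there is no bias without an effect. Unequal leaving is possible in a double-blind trial, but nothing in the text points to it. The larger figures need exactly the worst responders to leave. The chi-squared illustration is built near 0.05. All of this stands as a limit on size. It does not touch the mislabelled analysis set.

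A reader might infer that withholding laxatives with no rescue has materially biased this trial. The documents do not support that: they give no departures, no reasons and no split by arm.

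A reader might also infer that the protocol has no stopping provision and leaves patients untreated. That goes too far. Treatment lasts 7 days in patients already constipated for weeks. Criterion 5.7 bars bowel-altering medication at entry, so no current laxative is withdrawn. Obstruction and critical illness are excluded (5.1, 5.4), section 10.3 includes an entry examination, and inpatients are under ward care. Patients may withdraw, and the side-effect rule in 8.2 is broad enough that severe cramps or pain could be handled under it. Section 7 does not expressly forbid care after withdrawal. The flow chart and Appendix E cannot be read and may contain a step. What remains is narrower: no readable passage names worsening constipation or suspected obstruction as a reason to stop and treat.

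**Conclusion.** The point holds for the analysis set. As written, the SAP describes a completers analysis under an intention-to-treat label, and the nature of the outcome makes exclusion for outcome-related reasons plausible. This part rests on the wording alone.

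The size and direction of any bias cannot be known from the documents. A benefit is slightly understated under a common leaving rule. The bias can go either way, and be larger, if the arms leave unequally or the worst responders leave. Every figure rests on assumed means, leaving shares, arm sizes and improver counts. No claim about power is made: in simulation at 40 per arm with q = 0.4, power was 0.775 with no loss, 0.727 with random loss of the same shares and 0.708 for completers, so most of the fall is simply fewer patients.

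The change should be made because it is cheap and the label is wrong, not because a large bias has been shown. The safety wording is secondary.

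**What to change.** Replace the SAP's exclusion passage with:

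> All randomised patients are analysed in their assigned arm, using all diary days recorded, including days after stopping study product or taking a laxative or enema where available. In the chi-squared tests, patients without a day-7 result are counted as not improved. The completers-only result is reported as a per-protocol sensitivity analysis.

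Keep worst rank in the Mann-Whitney tests as a further sensitivity analysis, not the only primary rule, for the reason shown in step 5 of the working. Define non-compliance for the per-protocol set, and say whether the chi-squared tests use a continuity correction.

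In sections 9.2 and 10.5, collect the diary from patients who leave early, and add a laxative or enema box to the diary. As a secondary safety change, state in section 6 that suspected obstruction, vomiting or new severe abdominal pain is a reason to stop study product and treat under usual care.

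The cost is one SAP passage, a few protocol lines, one diary box and some effort to retrieve diaries. The estimate may be more conservative, and data from early leavers will sometimes be incomplete. The SAP is written in the past tense. If the data are already collected, only the SAP part can still be changed, and it is still worth doing.

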Official Title of the study:

Evaluation of the efficacy of probiotics in treating constipation in elderly patients with multiple chronic co-morbidities: a randomized control trial

NCT no: Nil

Date of Document:

22nd July 2019

Study Protocol

1. Study design

This is a randomized double-blinded clinical trial study.

2. Study population and subjects

Background and selection of study centers

The study will be conducted at the outpatient clinics, medical and surgical wards in Universiti Kebangsaan Malaysia Medical Centre.

3. Target population

- 3.1 The target populations are older patients aged 60 years or above with at least 2 chronic medical illnesses (Appendix A) and who complain of constipation that persists for several weeks or longer.
- 3.2 These patients are those who attending the medical/surgical outpatient clinics or being admitted to the medical/surgical wards in UKM Medical Centre during the study period.

The participants will be assigned to either interventional group or control randomly and the random selection is pre-determined prior to recruitment.

4 Inclusion criteria.

- 4.1 Elderly patients aged 60 years or above and able to give consent.
- 4.2 Patients who complain of constipation as per Mayo's clinic definition:
"Infrequent bowel movements of fewer than three bowel movements per week or difficult passage of stools that persists for several weeks or longer". (13)
- 4.3 Patients who have at least 2 chronic illnesses such as Diabetes Mellitus, Hypertensions, Chronic Kidney disease, Chronic Lung disease, or any medical illness which are prone to have constipation.

5. Exclusion criteria.

- 5.1 Patients with constipation of organic cause such as colorectal carcinoma, colonic ischaemia, inflammation, post radiation stricture, obstruction or presence of external compression.
- 5.2 Patients with constipation of neurological causes such as cerebrovascular disease and stroke, Parkinson's disease, autonomic neuropathy and spinal cord lesions.
- 5.3 Patients who are taking calcium supplements more than 1500mg a day.
- 5.4 Patients who are immune-compromised or critically ill.
- 5.5 Patients who are on opioid analgesia.
- 5.6 Patients with psychiatric illness.
- 5.7 Patients who are on any form of medications at point of entering the study that altered the normal bowel movement (either decreasing or increasing the peristalsis of the gut)
- 5.8 Patients who refuse to enter or consent for the study.

6. Subject withdrawal and Drop out

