8.1 Primary end point

A completed questionnaire on patient's demographic and medical illness data, stool output/day, stool consistency per output/day and constipated related symptoms scoring/day over the period of 7 study days.

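### An undefined non-compliance exclusion could remove patients who took a laxative, despite the intention-to-treat label, and no labelled form field records such use in days 1 to 7

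*Combined protocol and SAP*

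**What the plan says.** **Other treatment.** Section 7 states "No other treatments such as laxatives or enemas are given to all patients". Exclusion 5.7 keeps out "Patients who are on any form of medications at point of entering the study that altered the normal bowel movement", which is a condition at entry. The assigned regimen is "Dosage: 1 sachet twice a day after meals for 1 week".

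**Leaving the study.** Section 6 gives two reasons for withdrawal. One is that the patient withdraws consent; the other is "Patients will be withdrawn from the study if they experience intolerable or excessive side effects due to the probiotics". It does not mention other treatment, and it does not say that the list is complete.

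**Who is analysed.** The last paragraph of the SAP begins "Intention to treat analysis was used in this trial, where only the final results within the group which they were randomized" and goes on to say that those "receiving the treatment and completed the treatment assignment were analysed". Its final sentence is "Participants who deviates from the protocol as being non-compliance or withdrew consent were not included into the analysis".

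**What is recorded.** Section 8.1 lists demographic and illness data, stool output, stool consistency and "constipated related symptoms scoring/day over the period of 7 study days"; it does not list treatment use. The Appendix B diary takes symptom scores and Bristol marks. Appendix C lists laxatives, probiotics, high-fibre diets and enemas under the heading of previous treatment. Appendix D has one item on needing an enema or manual help. Sections 9.2 and 10.4 place the questionnaire at the start and make the diary the daily record, collected on day 7.

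**The concern.** Patients enter with persistent constipation and are meant to have no other bowel-active medication. Over the 7 days some may start a laxative or enema themselves. The plan does not say how such a patient is classed. Under one reading of the SAP that patient is removed after randomisation, which an intention-to-treat analysis is meant to prevent. The reason for removal may be linked to outcome, if those whose constipation persists are the ones who reach for a laxative; that link is an assumption.

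The recording gap makes this worse. Without a field for such use, any removal would depend on who happened to mention it, and the analyst would have to decide case by case. A later reader could not tell how many users there were in each arm. For outpatients in particular, this could not be reconstructed afterwards.

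**Working it through.** The documents state no figure to reproduce on this point, so the check compares the texts, counts the fields and adds one illustration under stated assumptions.

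**1. One patient followed through the plan.** Take a patient who uses every sachet, 2 per day × 7 days = 14, and takes a laxative on day 4.

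- Section 6: 0 of the 2 listed withdrawal reasons applies. Nothing listed takes the patient out before the diary is collected.
- SAP, sentence on those who received and completed treatment: the patient qualifies and is kept.
- SAP, exclusion sentence: the result depends on two readings.

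| Section 7 read as | Non-compliance read as | Patient |
|---|---|---|
| What the trial supplies | Either meaning | Kept |
| A bar on other treatment | Missed sachets only | Kept |
| A bar on other treatment | Any departure from the protocol | Removed |

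One of the three rows leads to removal. The text rules out none of them, because the term is undefined.

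**2. Fields that could record use in days 1 to 7.**

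- Appendix B as read has 14 columns: day (1), symptoms (5), one without a readable heading (1) and Bristol types (7). Labelled data columns: 5 + 7 = 12. Columns for other treatment: 0 of 12. The column for other entries sits under the symptoms heading, and the instruction covers only symptom scores and Bristol marks.
- Appendix C names 4 treatments, all as previous treatment. Recorded during days 1 to 7: 0 of 4.
- Appendix D has one enema item, with no 7-day window and no laxative item. If the questionnaire were repeated on day 7, at most 1 of the 4 would be captured. Section 8.1 speaks loosely of a questionnaire over the study days, but no text provides for a repeat.

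**3. Illustration of what exclusion can do (all rates assumed).** Suppose 60% respond on probiotic and 40% on placebo among all randomised, with users of other treatment counted as non-responders. Dropping users changes each arm's rate to p / (1 − r), where r is the share of users in that arm.

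| Users, probiotic / placebo | Rates after dropping users | Difference (all randomised: 20.0 points) |
|---|---|---|
| 5% / 5% | 63.2% / 42.1% | 21.1 points |
| 5% / 10% | 63.2% / 44.4% | 18.7 points |
| 5% / 20% | 63.2% / 50.0% | 13.2 points |
| 10% / 30% | 66.7% / 57.1% | 9.5 points |

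The difference can move either way. The table shows only that the rule can matter. It does not estimate this trial's bias: the SAP compares medians for stool frequency and consistency, defines no responder, and gives no rate of use.

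**The case against.** The strongest reply is that removal needs two doubtful readings together. Section 7 literally describes what is given to patients, and no readable text tells them not to treat themselves. Non-compliance comes directly after a sentence about receiving and completing the assigned treatment, so missed sachets are its natural meaning. On that view the two SAP sentences agree and our patient is kept. This stands as far as it goes: it makes removal a possibility, not a stated rule. It does not settle the matter, since a term that decides who is analysed should not have to be inferred from its neighbour.

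It is also fair that the underlying fault is the SAP's general departure from intention to treat, of which laxative use is only one route. The fix is therefore placed inside that wider correction. The recording gap remains even after everyone is analysed as randomised.

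The flow chart, parts of Appendix D and the consent form are not available, and one diary column has no readable heading. The claim is accordingly limited to labelled fields in the readable forms. Ward records might recover some use among inpatients, though no readable text provides for using them.

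A reader might go further and infer that the plan forbids self-treatment and discards laxative users, or that the result is thereby tilted towards the probiotic. The documents support neither. The ban is an inference from section 7, and the discard is an inference from an undefined word. With blinding intact and no treatment effect, removals for this reason should be about equal by arm, so no false-positive result is claimed.

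**Conclusion.** The point holds in a limited form. The SAP's exclusion sentence contradicts its intention-to-treat label, and because non-compliance is undefined it could reach a fully adherent patient who also took another constipation treatment. No labelled field in the readable forms records such use during days 1 to 7.

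Removal depends on reading section 7 as a bar and non-compliance as wider than missed sachets. That section 6 lets the patient continue assumes its two reasons are the only ones. A link between use and poor outcome is assumed. No size or direction of bias can be given from the documents. This is a low-priority point: desirable to fix, and cheap.

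**What to change.** **SAP.** As part of correcting the analysis to include all participants as randomised, replace the exclusion sentence with wording such as: *Use of a laxative, enema, fibre supplement or other probiotic during days 1 to 7 does not remove a participant. Such participants are analysed in their randomised arm with all diary days. The number of known users is reported by arm.* If the term non-compliance is kept for description, define it.

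Counting users as non-responders is an alternative, but it requires knowing who they are, which the present forms do not show. Keeping them with all their diary data can be done without that knowledge and matches the plan's own label.

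**Diary.** If diaries are still in use, add one Appendix B column: *Laxative, enema, fibre supplement or other probiotic today? No / which.* The SAP is written in the past tense, so this may come too late. In that case, report the missing record as a limitation and give only the users who happened to be reported.

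**Cost.** One replaced SAP sentence and, if possible, one diary column. The column adds slight burden and may prompt some use. Keeping users in means that the estimate includes any effect of their other treatment.
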